### **Total study duration**

Depending on the number of patients, the expected total duration of the study until the inclusion of the last patient is approximately 6 months.

## 11. Risk-benefit analysis

### All study related risks

Based on the classification criteria for medical devices (Directive 93/42/EEC, Annex IX), the optoacoustic system of iThera Medical corresponds to Class IIa:

- Active diagnostic device
- non-invasive
- Temporary use (<60 min)

No CE certification is available for this research device (current type designation according to imprint: Acuity Echo). A conformity assessment procedure in the sense of the MPG is not intended or planned by the manufacturer at the present time. It is therefore a purely scientific pilot study. There is no dependency on the manufacturer, all diagnostic and analytical procedures are available to the study directors on site.

### Adherence to energy levels

The laser safety and maximum permitted radiation dose for irradiation with laser pulses is regulated in the laser standards ANSI and IEC 60825. The MSOT system meets these standards and therefore remains below the MPE (maximum permissible exposure) limits for skin irradiation and is therefore considered safe.

### Temperature increases due to MSOT in tissue

Optoacoustic imaging does not result in any significant temperature increase in the tissue. The absorption of a laser pulse in the tissue results in a local transient temperature increase of a few millikelvin. Depending on the duration of the examination and the skin type of the patient, temperature increases occur typically in the range of less than one degree Kelvin.

### Histological changes in tissue

Histological changes in the target tissue and surrounding structures are neither expected nor have they been observed in previous preclinical and clinical studies.

Slight, reversible redness or warming might occur in very sensitive skin.

Such side effects are to be noticed at any time by the test person or doctor; the examination can then be interrupted or aborted. In any case, no irreversible damage is to be expected.

In general, the near infrared light used in the MSOT can lead to retinal damage if the eye is irradiated. In order to prevent this, test participants and examiners will wear appropriate laser safety glasses during the examination.

Since the data obtained is not used to interpret diagnostic results, there is no risk of possible misdiagnosis or incorrect display of data in this exploratory pilot study.

No other risks exist for this study, nor have we described any risks based on our own preliminary data.

### **Benefits associated with the study**

The data obtained in this study can provide important information about the changes of quantitative MSOT signal in muscles due to physical exercise, as well as over time. The quantifiable differences could be important for future planning of further studies and the avoidance of errors in the study design. Additionally, first longitudinal data are essential to design appropriate studies.

### **Termination criteria**

#### ***Termination criteria for the individual participant:***

Participation in the study is terminated if there is noticeable warming or reddening of the skin. The examination time per anatomical region is limited to 5 minutes, making these events highly unlikely.

Due to the short duration of the study participation, no other discontinuation criteria are planned.

#### ***Termination criteria for the whole study:***

A termination of the entire study is not planned.

### **Statement on medical justifiability**

Given to previous experience, especially with children, the risk of undesirable events is considered as extremely low.

No serious incident has been reported so far, neither at our site - nor in the literature. The majority of reported (foreseeable) problems are related either to the use of ultrasound gel for examination or the need to wear eye protection. The use of filter glass also explains the reported red visibility. This phenomenon was reversible within seconds. Table 1 shows the reported events from our study (MSOT\_DMD, 67\_18 B).

	Muscular dystrophy Duchenne N=10	Healthy volunteer N=10
Reversible adverse events- no.(%)		
Pressure of safety goggles	2 (20%)	
Coolness of Ultrasound-gel		4 (40%)
Red cast view		1 (10%)
Serious adverse events- no.(%)	0 (0%)	0 (0%)

**Table 1 – Adverse events**

Only measurements of extremities and no central organs are examined in this study - this leads to a further significant reduction of a possible residual risk. Particularly in light of the background of completely new therapeutic approaches, we hope that this method will provide us with a child-friendly diagnostic tool for the treatment of complex muscular diseases.

## 12. Biometrics

### **Explorative study: explanation of the statistical methodology, justification of the selected number of cases**

#### ***Case number calculation:***

As this is a pilot study and no information on the expected differences between the different groups is available yet, no case number calculation was performed. The number of cases given represents an estimate.

#### ***Statistical methods:***

The data are given as mean value with standard deviation. Correlations are specified with the parametric Pearson correlation coefficient (R). According to the distribution between timepoint 1 and timepoint 2, the differences of the mean values are statically examined with a parametric T-test. In all analyses, an error level of <0.05 is considered statically significant.

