**Primary objective:**

- Comparison of the quantitative proportion of hemo/myoglobin and collagen signal in muscle tissue of healthy subjects before and after physical exercise (6-MWT) determined by MSOT, as well as over time.

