**Secondary objectives:**

- Comparison of the quantitative amount of hemo/myoglobin and collagen signal determined by MSOT in muscle tissue of healthy volunteers at timepoint 1 and timepoint 2 after two weeks
- Comparison of the quantitative proportion of oxygenated/deoxygenated hemo/myoglobin signal in muscle tissue of healthy volunteers at timepoint 1 and timepoint 2 after two weeks
- Comparison of the MSOT-determined quantitative amount of hemo/myoglobin and collagen signal at three muscle positions of two muscles (quadriceps femoris and gastrocnemius)
- Comparison of the quantitative proportion of oxygenated/deoxygenated hemo/myoglobin signal determined by MSOT in three muscle positions of two muscles (quadriceps femoris and gastrocnemius)
- Comparison of the quantitative proportion of hemo/myoglobin and collagen signal determined by MSOT in muscle tissue of healthy female and male volunteers
- Comparison of the quantitative proportion of oxygenated and deoxygenated hemo/myoglobin signals determined by MSOT in muscle tissue of healthy female and male volunteers
- Correlation of the hemo/myoglobin and collagen signal determined with MSOT with the 6-MWT
- Correlation of the oxygenated/deoxygenated hemo/myoglobin signal determined by MSOT with the 6-MWT
- Comparison of the quantitative amount of hemo/myoglobin and collagen signal determined by MSOT between two independent examiners

- Comparison of the quantitative amount of hemo/myoglobin and collagen signal determined by MSOT between two images of one examiner

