## 7. Target parameters

All measurements with MSOT are performed at three muscle positions of the proximal and distal lower extremity muscles in lateral comparison (right - left, leg proximal: Musculus quadriceps, distal: Musculus gastrocnemius) by two different examiners, in healthy subjects, at two different timepoints.

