### Measurements

[figure not shown]
After informing of the subjects, all study participants are imaged by MSOT at 3 positions of 2 anatomical muscle regions on both sides (right and left): upper/lower leg, on predefined muscle groups (leg proximal: Musculus quadriceps, distal: Musculus gastrocnemius). The examination is performed by two independent examiners directly one after the other. The examination is performed analogous to sonography over the corresponding skin layers without further invasive procedures. The anatomical region can be localized by means of built-in B-scan sonography; the corresponding optoacoustic signals can be recorded in parallel. Each examiner performs two repetitive scans per muscle position. The duration per anatomical region is limited to 5 minutes; this corresponds to a maximum of 20 minutes for both lower extremities. The subjects can remain in a relaxed body position during the examination; assistance in the form of breathing manoeuvres or similar is not necessary. Subsequently, a 6-minute walk test is performed to test muscle activation. Afterwards another examination with MSOT is carried out analogous to the above mentioned procedure. The same procedure is repeated after 14 days.

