Non-invasive molecular imaging to determine the hemoglobin and collagen content in muscles before and after physical exercise and over time (MSOT_muscles)

Unique Protocol ID: 169_19B

ClinicalTrials.gov Identifier: NCT03979157

Version date: 23.04.2019

Sponsor:

Department of Pediatrics and Adolescent Medicine
University Hospital Erlangen
Friedrich-Alexander-University (FAU) Erlangen-Nürnberg
Pediatric Experimental and Translational Imaging Laboratory (PETI-Lab)
[name]
[name]
[contact]

Statistical Analysis Plan

The present study is a pilot proof-of-concept study. Due to lack of clinical trials in this area, the comparative changes of MSOT spectra and signals within and between examiners, before and after exercise, over time and between different muscles and muscle positions are unknown. Therefore, no sample size calculation was performed.

The primary outcome measure is to assess the reproducibility of the muscular optoacoustic spectra of healthy volunteers facing different variables (examiner, time, exercise, muscle position).

MSOT signals are derived from averaged video captures (seven frames) obtained in anatomical independent muscle regions in patients. All anatomical locations are considered independent. In cases of multiple scans/recordings, a mean of all analyzed scans is calculated.

Continuous variables are given as means and standard deviations; categorical variables are provided as numbers and percentages. Data are tested for normal distribution using Shapiro-Wilk test prior to inferential analysis. MSOT signals are compared matched manner using a paired t-test when parametric and a Wilcoxon matched-pair signed rank test when non-parametric. For the comparison of three or more groups analysis of variance (ANOVA) and for nonparametric distribution Friedman Test is used. Correlations are specified with the parametric Pearson correlation coefficient (r) and the nonparametric Spearman correlation (r_s), using a 95% confidence interval. Additionally, the intraclass correlation coefficient (ICC) will be used with the grading proposed by Landis and Koch. For all analysis an error level of $p < 0.05$ is considered as statistically significant. All analyses are performed using GraphPad Prism (Version 8, GraphPad Software, La Jolla, CA, USA) and/or IBM SPSS Statistics (Version 24, IBM Corp., N.Y., USA).

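### Every analysis uses p<0.05 with no designated primary test, testing order or adjustment, and the two-week comparison is both a primary and a secondary objective

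*Protocol*

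**What the plan says.** Protocol section 12, Statistical methods, ends with the rule: "In all analyses, an error level of <0.05 is considered statically significant". The SAP says that p below 0.05 "is considered as statistically significant" in all its analyses. On method it says: "MSOT signals are compared matched manner using a paired t-test when parametric". It provides a Wilcoxon alternative, and ANOVA or Friedman for three or more groups. Neither document mentions multiplicity, an order of testing or a single primary test.

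The primary objective in protocol section 6 compares hemo/myoglobin and collagen "before and after physical exercise (6-MWT) determined by MSOT, as well as over time". The first secondary objective compares the "hemo/myoglobin and collagen signal determined by MSOT in muscle tissue of healthy volunteers at timepoint 1 and timepoint 2 after two weeks". The SAP describes the primary outcome differently, as reproducibility across examiner, time, exercise and muscle position.

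On the amount of data, protocol section 7 states: "All measurements with MSOT are performed at three muscle positions of the proximal and distal lower extremity muscles in lateral comparison". Section 10, Measurements, adds a scan before and after the 6-minute walk, and then: "The same procedure is repeated after 14 days". The SAP averages multiple scans and treats anatomical locations as independent. It does not say whether locations are tested one by one or pooled.

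Section 6 of the protocol calls the study exploratory. Sections 9 and 12 and the SAP call it a pilot. The sample is 10 volunteers, with no sample size calculation.

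**The concern.** The plan separates primary from secondary objectives and lists 15 hypotheses, but gives every p-value the same label. A reader of the results could not tell which one answers the primary question. The candidates are two signals, two contrasts and, in the SAP, a reproducibility outcome covering four factors. The choice could be made after the data are seen.

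The protocol wants the results for planning studies in children with neuromuscular disease. A chance finding at p<0.05, reported as a significant change after walking or over two weeks, could shape the timing or choice of measurements there. Because the two-week comparison sits in both tiers, its status is undefined.

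**Working it through.** **Inputs from the documents.** Level 0.05 for every analysis (protocol section 12; SAP). Ten volunteers (section 9). Two primary signals (section 7) and two primary contrasts (section 6). Locations: 3 positions x 2 muscles x 2 sides = 12 (sections 7 and 10).

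**Assumptions.** Two-sided tests (sidedness is not stated), no true change in any signal, and a common correlation between tests. The documents give no correlations, so a range is shown.

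**Step 1: the plan's own figure.** There is no derived figure to reproduce: 0.05 is a chosen level and 10 is described as an estimate. For one valid test the chance of a false positive is 1 - 0.95^1 = 0.05, as stated.

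**Step 2: the primary objective, independent tests.** The chance of at least one false positive in k tests is 1 - 0.95^k.
- Two signals, before/after the walk: k = 2, 1 - 0.95^2 = 0.0975.
- Two signals x two contrasts: k = 4, 1 - 0.95^4 = 0.1855.

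**Step 3: correlated tests.** Tests within the same volunteers are likely to be correlated. Simulated paired t-tests with n = 10 (10,000 replicates) gave:

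| Tests | Correlation 0 | 0.5 | 0.8 |
|---|---|---|---|
| 2 | 0.09 | 0.10 | 0.08 |
| 4 | 0.18 | 0.16 | 0.12 |

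The four primary contrasts therefore carry about 12% to 19%, taking the exact 0.1855 at correlation 0. Each single test in these runs kept an error of 0.048 to 0.052.

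**Step 4: the locations, under two possible readings.**
- Tested separately: 2 signals x 12 locations = 24 before/after tests at one visit. Then 1 - 0.95^24 = 0.708 if independent. The simulated values are 0.49 at correlation 0.5 and 0.27 at 0.8.
- Pooled as independent: 12 locations x 10 volunteers = 120 pairs in one test. That single test then has a simulated error of 0.05 at within-person correlation 0, 0.18 at 0.1, 0.35 at 0.3, 0.45 at 0.5 and 0.54 at 0.8.

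The documents fix neither reading. One value per volunteer avoids both: it gives 10 differences and one t-test on 9 degrees of freedom.

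**Step 5: direction of the hypotheses.** Of the 15 hypotheses in section 6, two predict a difference: total, and oxygenated/deoxygenated, hemo/myoglobin before and after the walk. The other 13 predict none. Of the two primary signals, only hemo/myoglobin is expected to differ, and only across the walk.

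**The case against.** The strongest reply is that this is a declared exploratory pilot in 10 volunteers. Unadjusted tests are acceptable in such a study, and neither document claims to control error over the whole set. That stands, and it rules out demanding a correction across everything. It does not answer the point about labelling: the plan never says its p-values are unadjusted, and it calls each one below 0.05 significant without qualification.

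A reader might infer that the 5% level holds for no claim in the study. The documents do not support this. The level is stated per analysis, and a valid, pre-specified single test keeps it. A reader might also infer that listing the two-week comparison twice adds error. It does not, because it is the same comparison; only its status is unclear.

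A reader might also count every signal, location and visit and quote false-positive chances of 70% or more. The text does not say that locations are tested separately. The SAP's independence statement could equally mean pooling, and the three positions could share one ANOVA or Friedman test. Full independence is also unlikely for sites within one person. The 24-test figures show what could happen and do not describe the plan.

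Finally, for the 13 hypotheses of no difference, a false positive would count against the sponsor's own expectation. That narrows the risk of a false claim of an exercise effect mainly to the two hypotheses that predict one. It does not show which result is primary. Nor would p above 0.05 establish agreement, which is a further reason to report intervals.

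**Conclusion.** The point holds in a limited form. The plan has no single primary test and no control of error over the set, and it places one comparison in two tiers. For the four contrasts in the primary objective, the chance of at least one false positive is about 12% to 19%. This assumes no true change, two-sided paired t-tests in 10 volunteers and correlations from 0.8 down to 0. For the two signals before and after the walk alone it is about 8% to 10%.

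The error of a valid single test is not in doubt on multiplicity grounds. It would be in doubt if the 12 locations were pooled as independent, and the SAP leaves that possible. This is a cheap improvement to an exploratory plan and does not invalidate the study.

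**What to change.** In protocol section 12 and the SAP, reserve the unqualified term statistically significant for one named test. A natural candidate is the before/after-walk change in hemo/myoglobin at timepoint 1, since this is the only primary signal for which a difference is hypothesised. Use one value per volunteer before and one after the walk, each the mean over locations, examiners and repeat scans, and do not treat locations as independent.

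Report every other comparison, including collagen, the two-week comparison and the reproducibility comparisons, as an estimate with a 95% confidence interval. Label any accompanying p-value exploratory and unadjusted.

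List the two-week comparison in one tier of protocol section 6; the sponsor can choose which. Align the SAP's primary outcome sentence with that choice and with the named test.

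The cost is text only, with no added volunteers, scans or visits. Fewer results may be called significant. Averaging over locations may also dilute a change confined to one muscle, which the location-level estimates and intervals would still show.

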## **13. Data management und and data protection**

### **Data acquisition and storage**

All raw data, such as patient files, are source documents. Their availability is ensured for routine monitoring. The participation of the individual patients or test persons in the study is documented. The study leader maintains an independent list for the identification of the participating patients. This list contains the names and date of birth as well as the date of examination and pseudonymisation codes of the patients and subjects. The study leader is responsible for the quality of data collection and storage. The data storage (complete data) takes place on computers or specially designed network drives of the University Hospital Erlangen. The raw imaging data (no patient-related data) are stored on dedicated servers of iThera Medical GmbH.

### **Pseudonymisation**

Prior to a scientific analysis of the materials and data of this study, all information will be pseudonymized according to the guidelines of the Federal Data Protection Act.

### **Data transfer**

A transfer of the data or biological material is not foreseen in this study and will not take place. The study results can be published anonymously, but it will not be possible to draw conclusions about the identity of the participating persons. The data is stored for 10 years and then destroyed.

### **Revocation, data deletion**

If the declaration of consent is revoked, data collected up to this point can be taken into account. The patient has the right to demand that the data be destroyed, provided that legal provisions do not prevent such destruction.

## **14. Handling of biomaterials**

No biomaterials are obtained.

## **15. Insurance**

The participants of the study are insured via the group contract of the CCS Erlangen.

Non-invasive molecular imaging to determine the hemoglobin and collagen content in muscles before and after physical exercise and over time (MSOT_muscles)

Unique Protocol ID: 169_19B

ClinicalTrials.gov Identifier: NCT03979157

Version date: 23.04.2019

Sponsor:

Department of Pediatrics and Adolescent Medicine
University Hospital Erlangen
Friedrich-Alexander-University (FAU) Erlangen-Nürnberg
Pediatric Experimental and Translational Imaging Laboratory (PETI-Lab)
[name]
[name]
[contact]

Statistical Analysis Plan

The present study is a pilot proof-of-concept study. Due to lack of clinical trials in this area, the comparative changes of MSOT spectra and signals within and between examiners, before and after exercise, over time and between different muscles and muscle positions are unknown. Therefore, no sample size calculation was performed.

The primary outcome measure is to assess the reproducibility of the muscular optoacoustic spectra of healthy volunteers facing different variables (examiner, time, exercise, muscle position).

MSOT signals are derived from averaged video captures (seven frames) obtained in anatomical independent muscle regions in patients. All anatomical locations are considered independent. In cases of multiple scans/recordings, a mean of all analyzed scans is calculated.

Continuous variables are given as means and standard deviations; categorical variables are provided as numbers and percentages. Data are tested for normal distribution using Shapiro-Wilk test prior to inferential analysis. MSOT signals are compared matched manner using a paired t-test when parametric and a Wilcoxon matched-pair signed rank test when non-parametric. For the comparison of three or more groups analysis of variance (ANOVA) and for nonparametric distribution Friedman Test is used. Correlations are specified with the parametric Pearson correlation coefficient (r) and the nonparametric Spearman correlation (r_s), using a 95% confidence interval. Additionally, the intraclass correlation coefficient (ICC) will be used with the grading proposed by Landis and Koch. For all analysis an error level of $p < 0.05$ is considered as statistically significant. All analyses are performed using GraphPad Prism (Version 8, GraphPad Software, La Jolla, CA, USA) and/or IBM SPSS Statistics (Version 24, IBM Corp., N.Y., USA).

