## 6. Study objectives

The aim of the proposed study is a longitudinal comparison of muscle tissue composition based on Multispectral Optoacoustic Tomography (MSOT) of healthy, adult subjects, before and after physical exercise.

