### **Primary target:**

Quantitative hemo/myoglobin and collagen signal (in arbitrary units)

*This target is measured non-invasively by MSOT.*

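### Protocol and SAP name different primary outcomes, and the SAP lists exercise among its reproducibility factors although the protocol predicts that hemo/myoglobin changes after the walk

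*SAP*

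**What the plan says.** **SAP.** The primary outcome is the "reproducibility of the muscular optoacoustic spectra of healthy volunteers facing different variables (examiner, time, exercise, muscle position"). Neither hemo/myoglobin nor collagen is named in it, although the SAP's own title refers to "hemoglobin and collagen content in muscles before and after physical exercise and over time". The analysis text plans paired tests, ANOVA or Friedman tests for three or more groups, correlations and, in addition, an ICC with the Landis and Koch grading. Where several scans exist, their mean is used.

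**Protocol, section 6.** The overall aim is a "longitudinal comparison of muscle tissue composition based on Multispectral Optoacoustic Tomography (MSOT) of healthy, adult subjects, before and after physical exercise". The primary objective compares hemo/myoglobin and collagen signal "before and after physical exercise (6-MWT) determined by MSOT, as well as over time".

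**Protocol, section 7.** The primary target is "Quantitative hemo/myoglobin and collagen signal (in arbitrary units").

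**Protocol, section 6, secondary objectives.** These include the comparisons of:
- "hemo/myoglobin and collagen signal determined by MSOT between two independent examiners"
- "hemo/myoglobin and collagen signal at three muscle positions of two muscles (quadriceps femoris and gastrocnemius")
- "signal determined by MSOT in muscle tissue of healthy volunteers at timepoint 1 and timepoint 2 after two weeks"

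They also include a comparison of two images taken by one examiner.

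**Protocol, sections 3 and 5.** The closing paragraphs state the pilot's aim without ranking: whether exercise alters haemoglobin, whether collagen stays constant, and whether repeated measurements agree across positions, examiners and time.

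**The concern.** The two documents give different answers to the question of what the primary result is. A mean change in two signals and the reproducibility of spectra are different estimands, and they lead to different headline numbers. If the choice stays open, it can be made after the data are seen.

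Placing exercise in the same list as examiner, time and position adds a problem of interpretation. For a true reproducibility factor, a difference counts against the method. For exercise, the protocol expects hemo/myoglobin and oxygenation to move, so a difference there would show that the method detects physiology.

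Protocol section 11 says the results are meant to help plan later studies and avoid design errors. A real exercise effect read as poor repeatability, or repeatability never isolated because scans were averaged first, would mislead that planning.

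**Working it through.** **1. The statements side by side.** Ranks come from the objectives in protocol section 6 (hemo/myoglobin and collagen). Predictions come from the hypotheses in the same section.

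| Factor | Protocol rank | Prediction: hemo/myoglobin, oxygenation | Prediction: collagen | SAP rank |
|---|---|---|---|---|
| Exercise (6-MWT) | primary | change | no change | primary |
| Two-week interval | primary and secondary | no change | no change | primary |
| Muscle position | secondary | no change | no change | primary |
| Two examiners | secondary | no change | no change | primary |
| Repeat scans, one examiner | secondary | no change | no change | not named separately |

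The documents overlap on exercise and time. They differ in the quantity (signal change or reproducibility) and in the rank of position and examiner. Of the 15 hypotheses, 2 predict a difference, and both are exercise hypotheses (hemo/myoglobin and oxygenation). The other 13 predict none. Exercise is thus the only factor for which the protocol expects a change.

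**2. Scan averaging.** Inputs are from protocol sections 7 and 10.
- Locations: 3 positions × 2 muscles × 2 sides = 12.
- Scans per examination: 12 × 2 examiners × 2 repeats = 48.
- Scans per volunteer: 48 × 2 (before and after the walk) × 2 visits = 192.

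Averaging the two repeats leaves 48 / 2 = 24 values per examination and none of the 24 repeat differences. If the mean also runs over examiners, 12 values remain and the examiner contrast is lost as well.

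**3. What grading exercise by ICC could do (illustration only).** The documents give no SD, ICC or expected shift. Assume pre- and post-walk readings enter one absolute-agreement ICC, within-state ICC r, total SD 1, and the same shift d in every volunteer. Then ICC = r / (1 + d²/2).
- r = 0.80: d = 0.5 gives 0.80 / 1.125 = 0.71; d = 1.0 gives 0.80 / 1.5 = 0.53.
- r = 0.60: 0.53 and 0.40.
- r = 0.90: 0.80 and 0.60.

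A consistency ICC stays at r and does not show the shift at all. Simulation at r = 0.80 agreed with the formula.

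**4. Why p≥0.05 does not show constancy.** With 10 volunteers and, as an assumption, one value each, the 95% CI half-width for a mean paired change is t(0.975, 9)/√10 = 2.262/3.162 = 0.72 SD of the paired differences. Even an observed change of zero would leave true changes of up to about 0.7 SD in either direction compatible with the data. Under the SAP's assumption that locations are independent (10 × 12 = 120 values), the half-width would be about 0.18 SD. The precision therefore depends on an analysis unit that the two readings treat differently.

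**The case against.** The best defence is that the SAP condenses an aim the protocol itself states. Its four factors match those listed in protocol sections 3 and 5 as not yet investigated, and 12 of the 15 hypotheses concern time, position or examiner. Reproducibility under different variables can also be read as measuring how far each variable shifts the signal. The SAP introduces paired tests first and the ICC only as an addition. The study is an exploratory pilot with no sample size calculation.

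Much of this stands. A reader might infer that the SAP alone departed from a clear protocol; the unranked aim in the protocol's summary and background does not support that. A reader might also infer that the SAP plans to pool pre- and post-walk scans in one ICC. It does not say so, and the falls in step 3 need that pooling, an absolute-agreement form, and assumed values for r and d. Nor do the documents support a claim that the study is underpowered by a stated amount: they give no variance, and the answer changes with the analysis unit. The unstated ICC form and the absence of a pass threshold are missing detail, not errors. For collagen, exercise fits a reproducibility reading.

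The defence does not remove the conflict. An exploratory design excuses the missing sample size calculation, but not two different primaries, and the broader reading of reproducibility still does not separate an expected change from an unwanted one.

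**Conclusion.** The point holds in limited form. Four parts rest on the text alone:
- The primary outcomes differ between the documents.
- The protocol is itself not consistent on rank, and it lists the two-week comparison as both primary and secondary.
- For hemo/myoglobin and oxygenation, exercise is an expected effect and should not be graded as reproducibility.
- The averaging rule, if applied throughout, removes the variation that the within-examiner objective sets out to compare.

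The numerical consequence is not established. The ICC fall from 0.80 to 0.71 or 0.53 only illustrates an analysis that the SAP does not state. The 0.72 SD half-width assumes one value per volunteer; it supports the general caution about non-significant results and says nothing firm about this study's precision. The contradiction should be corrected, but the small exploratory scope limits the harm.

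**What to change.** 1. State the same primary outcome in the protocol (sections 6 and 7) and the SAP. Either choice is acceptable. If the protocol's is kept, define both the exercise and the time contrast for hemo/myoglobin and collagen. If the SAP's is kept, rewrite the protocol's primary objective and primary target to match.
2. List the two-week comparison once, as primary or secondary.
3. Under either choice, analyse exercise as an effect: the within-volunteer paired change, after minus before the walk, with a 95% CI, separately for each signal.
4. Compute ICCs for examiner, repeat scan and two-week interval within one exercise state. Use unaveraged scans for the repeat-scan ICC, and limit the averaging rule to the other analyses. The ICC type can be stated in the same sentence.
5. For hypotheses of no difference, collagen after exercise included, report the CI and do not conclude no change from p≥0.05.

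The cost is a few lines in each document, with no extra scans, volunteers or time. The downside is that one of the two current primaries loses that label.
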